**Statement of Compliance**

This study will be conducted in accordance with the Code of Federal Regulations on the Protection of Human Subjects (45 CFR Part 46), 21 CFR Parts 50, 56, 312, and 812 as applicable, any other applicable US government research regulations, and institutional research policies and procedures. The International Conference on Harmonization (“ICH”) Guideline for Good Clinical Practice (“GCP”) (sometimes referred to as “ICH-GCP” or “E6”) will be applied only to the extent that it is compatible with FDA and DHHS regulations. The Principal Investigator will assure that no deviation from, or changes to the protocol will take place without documented approval from the HRRC, except where necessary to eliminate an immediate hazard(s) to the trial participants. All personnel involved in the conduct of this study have completed Human Subjects Protection Training.

## List of Abbreviations

AE	Adverse Event/Adverse Experience
AGP	Aerosol Generating Procedure
CFR	Code of Federal Regulations
COVID-19	Coronavirus Disease
CQ	Chloroquine
CRF	Case Report Form
DHHS	Department of Health and Human Services
DSMB	Data and Safety Monitoring Board
FDA	Food and Drug Administration
GCP	Good Clinical Practice
HCQ	Hydroxychloroquine
HCW	Health Care Worker
HCWP	Health Care Worker Prophylaxis
HRPO	Human Research Protections Office
HIPAA	Health Insurance Portability and Accountability Act
ICF	Informed Consent Form
ICH	International Conference on Harmonization
ICU	Intensive Care Unit
IRB	Institutional Review Board
ISM	Independent Safety Monitor
MOP	Manual of Procedures
N	Number (typically refers to participants)
NIH	National Institutes of Health
OHRP	Office for Human Research Protections
OHS	Occupational Health Service
PCR	Polymerase chain reaction
PEP	Post exposure prophylaxis
PI	Principal Investigator
PI	Principal Investigator
PPE	Personal Protective Equipment
RA	Rheumatoid Arthritis
SAE	Serious Adverse Event/Serious Adverse Experience
SARS-CoV-2	Severe acute respiratory syndrome coronavirus 2
UNMH	University of New Mexico Hospital
UNMHS	University of New Mexico Health System

[figure not shown]
US United States  
 WHO World Health Organization

**Protocol Summary**

Title	Off label study to evaluate the efficacy of hydroxychloroquine as prophylaxis to prevent severe acute respiratory syndrome coronavirus 2 (SARS-CoV-2) infection among Health Care Workers (HCWs) who are at high risk of occupational exposure to SARS-CoV-2 Short Study Title: COVID-19 HCWP HCQ Study
Brief Summary	The HCW Prophylaxis (HCWP) Study, single, open and off label intervention study. Up to 350 participants will be assigned to group that takes HCQ or group that opts to not take study medication. Participants will be UNM HEALTH SYSTEM HCW at high risk for occupational exposure to SARS-CoV-2. Study timepoints will include Day 1 screening/enrollment, 30 day, 60 day, and 90 day assessments. Questionnaires will be collected in all timepoints.
Phase	Off label use of HCQ
Primary Objectives	To evaluate the efficacy of hydroxychloroquine (HCQ) for prophylaxis (HCWP) to prevent severe acute respiratory syndrome coronavirus 2 (SARS-CoV-2) infection among Health Care Workers High Risk of Occupational Exposure to SARS-CoV-2
Methodology	The Health Care Worker Prophylaxis (HCWP) Study, single, open and off label intervention study
Primary Endpoint	Number of HCW who test positive for SARS-CoV-2 while in the trial as determined by polymerase chain reaction assays from standard of care swaps.
Study Duration	12 months
Participant Duration	Participant Study period: up to 90 days for both groups, inclusive of those who elect to convert from Group B to Group A.
Duration of IP administration	Up to 90 days
Population	Total number of participants: Up to 350 UNM HEALTH SYSTEM health care workers with high risk of occupational exposure to SARS-CoV-2 Group A: up to 275 (HCW choose to be provided HCQ) Group B: up to 75 (HCW choose not to be provided HCQ)
Study Sites	UNM HEALTH SYSTEMS
Number of participants	Up to 350
Description of Study Agent/Procedure	Hydroxychloroquine- oral administration 
 
• Duration: up to 90 days or until meeting study termination criteria
 
• Loading dose: 600 mg once for the first day
 
• Maintenance dose: 200 mg, daily
 
 
Hydroxychloroquine is licensed for the chemoprophylaxis and treatment of malaria and as a disease modifying antirheumatic drug. It has a long history of being safe and well tolerated at typical doses. HCQ has antiviral activity in vitro against coronaviruses, and specifically Covid-19.

Key Procedures	Questionnaires

Statistical Analysis	All data will be summarized using appropriate descriptive statistics, including mean, median, standard deviation, and range for continuous variables and frequency and proportions for categorical variables. Data will also be summarized graphically. Distributional assumptions will be assessed with suitable transformation conducted if indicated. Significance tests will use two-sided Type I error rate of 0.05. The primary analysis will assess the number of HCW who test positive for SARS-CoV2 while on trial. Secondary endpoints include symptoms reported over time via web-based questionnaires, as well as other clinical endpoints such as quarantine, hospital admission, ICU admission, and mortality.
----------------------	--

## Schematic of Study Design

## 1 Background Information and Scientific Rationale

Severe acute respiratory syndrome coronavirus 2 (SARS-CoV-2) is a coronavirus novel to the human population discovered in December 2019; it is currently the cause of a global pandemic [1-3]. The World Health Organization (WHO) named the novel coronavirus severe acute respiratory syndrome coronavirus 2 (SARS-CoV-2) and the disease caused by SARS-CoV-2 coronavirus disease (COVID-19). As of 7 April 2020, person-to-person transmission has occurred worldwide, approaching 1.5 million cases and over 75,000 deaths. The WHO declared the COVID-19 pandemic a Public Health Emergency of International Concern on 30 January 2020 [4]. Most deaths and severe pneumonitis have occurred in the elderly or in persons with underlying pulmonary, cardiac, and other co-morbidities. SARS-CoV-2 infection can be asymptomatic, mild with self-limited pneumonia and other symptoms, or progress to life threatening respiratory involvement and multi-organ failure. The infection often appears less severe in children and younger adults [5]. Nevertheless, the burden to health and economic systems globally of this pandemic is already substantial and the pandemic has not peaked on a worldwide basis. No acquired immunity to this novel viral infection appears to exist in the human population globally and no effective treatment or preventative agent is licensed at this time.

An early report of 1700 cases of COVID-19 among health care workers (HCWs) caring for COVID-19 patients in China, included 5 deaths, in a published series of over 72,000 cases [6]. The number of HCWs infected with SARS-CoV-2 are increasing every day in USA and other countries.

On 3 March 2020, WHO declared a global shortage of personal protective equipment (PPE) leaving doctors, nurses and other frontline workers dangerously ill-equipped to care for COVID-19 patients [7]. By nature of their work caring for ill patients and evidence that SARS-CoV-2 can be transmitted from human-to-human, HCWs are at increased risk for COVID-19 infection. Many aerosol-generating procedures (AGP) are performed without knowing SARS-CoV-2 infection status. The SARS-CoV-2 epidemic has put tremendous strain on HCW

in all aspects. Scientists at the UNM HEALTH SYSTEMS are interested in studying the SARS-CoV-2 and strategies to protect HCWs in high-risk exposure settings.

As of today, there is no approved treatment or prophylaxis for SARS-CoV-2 by FDA (Food and Drug Administration). The FDA has issued an “emergency use authorization” for HCQ use <https://www.fda.gov/medical/136537/download>. HCQ is licensed for the chemoprophylaxis and treatment of malaria and as a disease modifying antirheumatic drug [8-9]. It has a long history of being safe and well tolerated at typical doses. HCQ has antiviral activity in vitro against coronaviruses, and specifically SARS-CoV-2. Pharmacologic modeling based on observed drug levels and in vitro drug testing suggest that prophylaxis at approved doses could prevent SARS-CoV-2 infection and/or ameliorate viral shedding. Based on in vitro data that HCQ inhibits viral replication and limited observations reported from China HCQ has the potential to prevent SARS-CoV-2 infection among HCWs at high risk of occupational exposure to SARS-CoV-2 [10-12].

However, at this time there is no in human data and we are unable to state if the drug will in fact decrease, have no effect or increase the chance of SARS-CoV-2 infection. This study is designed to answer whether prophylaxis with HCQ can mitigate the risk of SARS-CoV-2 infection among HCWs in high-risk settings.

#### **IND Exemption:**

- HCQ is lawfully marketed in the United States.
- The investigation is not intended to be reported to FDA as a well-controlled study in support of a new indication and there is no intent to use it to support any other significant change in the labeling of the drug.
- In the case of a prescription drug, the investigation is not intended to support a significant change in the advertising for the drug.
- The investigation does not involve a route of administration, dose, patient population, or other factor that significantly increases the risk (or decreases the acceptability of the risk) associated with the use of the drug product (21 CFR 312.2(b)(1)(iii)).
- The investigation is conducted in compliance with the requirements for review by an IRB (21 CFR part 56) and with the requirements for informed consent (21 CFR part 50)
- The investigation is conducted in compliance with the requirements of § 312.7 (i.e., the investigation is not intended to promote or commercialize the drug product).

## **2 Potential Risks & Benefits**

### **2.1 Benefits**

It is possible that HCQ will prevent positive SARS-CoV-2 conversion in HCW or reduce subsequent severity of infection. Additionally, medical societies and the general public may benefit from the information collected from this study.

### **2.2 Risks**

#### **2.2.1 Risk of study agent**

To account for possibilities of drug interactions, we have excluded a small list of anti-arrhythmic because of a theoretic concern of the effects on prolonged QTc interval. Additional drug interactions listed in the monograph are not expected to be clinically relevant at the doses and duration being prescribed. The PI's will monitor subjects who develop side effects. The only anticipated side effect we expect to see in 1-2% of the subject population is mild, self-limited drug reaction presenting as skin rash. More rarely, the drug has been associated with Stevens-Johnson Syndrome and Toxic Epidermal Necrolysis, therefore subjects who experience rash will be asked to discontinue HCQ. Additionally, dyspepsia may be encountered with drug administration – not ulcerogenic. This tends to be mild and self-limiting. The drug can be taken with food. Recommendation to subjects is to avoid antacids and cimetidine, as they reduce bioavailability. Alternatives include proton pump

inhibitors and other histamine 2 blockers. As with any experimental treatment for specific diseases, there may be unknown or unforeseeable side effects.

### 3 Objectives

Primary Objective	Primary Endpoint
To evaluate the efficacy of hydroxychloroquine (HCQ) for prophylaxis to prevent severe acute respiratory syndrome coronavirus 2 (SARS-CoV-2) infection among HCWs at high risk of occupational exposure to SARS-CoV-2 compared to eligible cohort that declines treatment	Frequency of infection with SARS-CoV-2 as determined by positive PCR for the virus on standard diagnostic tests.
Secondary Objectives	Secondary Endpoints
1. To characterize whether high-risk HCW who test positive for SARS-CoV-2 have an asymptomatic infection or report symptoms of COVID-19 in the 4 weeks preceding positive SARS-CoV-2	1. Symptom questionnaires performed once daily as currently mandated for HCW in high risk settings within UNMHS.
2. Determine role of occupational health exposure risk level on subsequent conversion frequency (mild-moderate-severe)	2. Online survey required once daily for all at risk HCW (existing document)
3. To assess the severity of any SARS-CoV-2 infection after prophylactic treatment with hydroxychloroquine.	3. Symptom questionnaires, Hospital admission rate, ICU admission rate, Mortality rate, PSI score of respiratory compromise
4. To assess the tolerability of hydroxychloroquine prophylaxis of SARS-CoV-2 in this population	4. Incidence of AEs or SAEs related to HCQ at study termination.
Exploratory Objectives	Exploratory Endpoints
1. To determine whether hydroxychloroquine reduces time lost from work	1. Days away from work
2. To assess the compliance of hydroxychloroquine prophylaxis	2. Frequency of missing dose
3. To assess whether HCQ benefits are different for specific AGPs or exposure on certain covid units (MICU v. ED v. covid rule out unit)	3. Frequency of positive test for SARS-CoV-2 related to AGP's or specific Covid-19 units.
4. To compare seroconversion between HCQ-treated and HCQ-untreated subjects on blood or plasma specimens.	4. Serological analyses at 4 times points (baseline, 30,60 and 90 days of study enrollment---with a 7-day window after each time point to complete analyses)

5. Metagenomic next generation sequencing of SARS-CoV-2 isolates detected in subjects	5. Sequence of viral isolates compared to published genomes and community-circulating SARS-CoV-2
---	--

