## 4.6 Participant Withdrawal or Termination

Reasons for early Withdrawal or Termination

- Participants become PCR-confirmed SARS-CoV-2 status
- Participant starts disallowed medication (Group A only)
- Advent of an adverse event which necessitates discontinuation of HCQ (Group A only, see section 6)
- Participant decides to withdraw from the study
- PI discontinues participation due to safety concerns
- Participant decides to withdraw consent
- Participant's primary care provider determines the study is not in participant's best interest
- PI decides to withdraw participant due to non-compliance

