## 5 Study Procedures and Schedule

### 5.1 Study Procedures/Evaluations

#### 5.1.1 Study Specific Procedures

##### Employee Exposure Survey and Aerosol Generating Procedures (Appendix A)

Participants from both Group A and B will be asked to complete the Employee Exposure Survey. This online instrument asks health care providers currently working in at risk units to report symptoms or exposures (eg. AGPs) related to their encounters with patients who have or are suspected of Covid-19. These HCWs are reminded to complete the Survey once per day. The link to this REDCap survey is currently being emailed to UNMHSC HCWs and they can access it through widely distributed QR codes. Given its active use, this survey will not add additional stress or workload to study participants. Additional study specific questions will be added to this survey and the data is linked to REDcap a database.

Confirmation of Pregnancy in Women of Childbearing Potential: We will document in subject's research record whether they are pregnant based on self-report and date of last menses (at Screening and follow-up visits). Pregnancy is not a contraindication for receiving HCQ.

A list of potential Aerosol Generating Procedures (AGP) is also provided in Appendix A.

Subjects will only be asked to complete SARS-CoV-2 testing at study enrollment and the 30, 60 and 90 day follow up points, with a 7-day window after each time point to complete the testing.

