### 5.2 Study Schedule

#### 5.2.1 Schematic of Study Design

##### Schematic of Study Design

**Schedules of Activities for COVID-19 HCWP HCW HCQ Study**

Task	Screening/ Baseline	Daily (existing required survey)	30 Day (± 7days)	60 Day (± 7days)	90 Day (± 7days)	Early Termination or Clinically Suspected SARS- CoV-2
Consent	X					
Health history	X					
Exposure Survey (online)	X	X				X
Swab* for SARS-CoV-2 and plasma/serum sample	X		X	X	X	X
Hydroxychloroquine dosing initiation	X					
Adverse Events		X	X	X	X	X

\*Lab has confirmed ability to test samples from week over next weekend. Estimate up to 50 total per week (25 Sat, 25 Sun). Lab has also agreed to bank plasma and serum samples for delayed analysis.

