### **5.2.4 Early Termination Visit**

Early termination visit will consist of questionnaire and nasal swab.

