### 7.4.3 Analysis of the Secondary Endpoint(s)

Secondary endpoints include symptoms reported over time via questionnaires, as well as other clinical endpoints such as hospital admission, ICU admission, and mortality. These binary clinical outcomes will be analyzed in a manner similar to that described above for the primary endpoint. Symptoms will be included as predictor variables. Antibody titers for SARS-CoV-2, measured as an exploratory endpoint in serum or plasma samples, will also be analyzed as binomial values. Positive values will be defined as a four-fold or greater increase in IgG antibody titers compared to baseline. Other descriptive analyses will be provided of the antibody titer results, including geometric mean, median, standard deviation, and titer range.

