## 8 Source Documents

Source data is all information, original records of clinical findings, observations, or other activities in a clinical trial necessary for the reconstruction and evaluation of the trial. Source data are contained in source documents. Information from clinical parameters will be obtained from the Symptoms Questionnaire. A separate electronic dataset (using REDcap) will be constructed to capture the most important clinical information on the patients including the following: demographic information (gender, age, DOB, place of residence, ethnicity and race), presenting and daily symptoms and signs (including fever, cough, SOB, sputum production, anosmia, hyposmia, fatigue, sore throat, nasal congestion, diarrhea, headache, vital signs, pulmonary auscultatory findings)

Each person participating in this Study will be assigned a randomly generated study ID that will be linked to identifiers (MRN, DOB) in a linking table to be kept separate from the research data. Data and specimens will

be labelled with the study ID only. Only HRRC-approved members of the study team who have the appropriate training will have access to the data and identifiers. All data that we collect in this study will be entered into REDCap, a secure data-base, on a password-protected computer using a secure network. Any hard copy records/data will be kept in a locked file cabinet in the locked office of a designated member of the Study team. The specimens will be kept and stored in the Clinical and Translational Science Center at the UNM HSC and can only be accessed by the members of the study team. Investigators will transport the specimens to TriCore Reference Laboratories for lab analysis through standard transport hospital procedures. Once data collection is complete, data will be de-identified by destruction of the linking table.

Access to study records will be limited to IRB-approved members of the study team. The investigator will permit study-related monitoring, audits, and inspections by the IRB/EC, government regulatory bodies, and University compliance and quality assurance groups of all study related documents (e.g. source documents, regulatory documents, data collection instruments, study data etc.). The investigator will ensure the capability for inspections of applicable study-related facilities (e.g. pharmacy, diagnostic laboratory, etc.).

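### Secondary objective 1 counts only symptoms in the 4 weeks before the positive test, so workers who fall ill after a positive scheduled swab are labelled asymptomatic

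*Combined protocol and SAP*

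**What the plan says.** Secondary objective 1 in Section 3 is to describe whether positive workers "have an asymptomatic infection or report symptoms of COVID-19 in the 4 weeks preceding positive SARS-CoV-2". The endpoint paired with it is "Symptom questionnaires performed once daily as currently mandated for HCW in high risk settings within UNMHS". No list of qualifying symptoms, onset interval or later follow-up is attached. Section 7.4.3, on the secondary endpoints, states "Symptoms will be included as predictor variables" and gives no rule for sorting cases into symptomatic and asymptomatic.

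On swab timing, Section 5.1.1 states "Subjects will only be asked to complete SARS-CoV-2 testing at study enrollment and the 30, 60 and 90 day follow up points", with 7 days allowed after each point. The schedule in Section 5.2.1 shows the follow-up visits at plus or minus 7 days and adds a swab at early termination or clinical suspicion.

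On what follows a positive result, Section 4.6 lists among the reasons for withdrawal or termination "Participants become PCR-confirmed SARS-CoV-2 status", and Section 5.2.4 says "Early termination visit will consist of questionnaire and nasal swab". Section 6.4 records non-serious adverse events until 7 days, and serious ones until 30 days, after the last day of participation.

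**The concern.** The scheduled swabs are taken without regard to symptoms, and participants must be symptom-free to enrol. These swabs are therefore where an infection can be caught before onset. A worker who is well at a positive day-30 swab and falls ill two days later has no symptoms in the preceding 4 weeks. Under the wording of the objective that infection is asymptomatic.

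The split between symptomatic and asymptomatic infection is the whole content of secondary objective 1. If pre-symptomatic cases are pooled with infections that never produce symptoms, the reported asymptomatic share has no clear meaning. Symptoms that start after the swab may not be recoverable at analysis if they were never collected.

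**Working it through.** **Step 1: is there a later assessment that corrects the label?** The documents give no event count, power or precision figure for this objective, so there is nothing to reproduce. The sections compare as follows.

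- Section 3, objective 1: the symptom window ends at the positive test.
- Section 4.6: PCR positivity is a reason for leaving the study.
- Section 5.2.4: the closing visit is one questionnaire and one swab, with no later symptom contact.
- Section 3, objective 3: symptom questionnaires also serve severity, but with no stated timing after the positive test and no link to objective 1.
- Section 6.4: adverse event capture continues for 7 days, again without a link to objective 1.
- Section 7.4.3: no classification rule.

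No section reclassifies a case on later symptoms.

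**Step 2: how many labels could be wrong?** All inputs here are assumptions. Let s be the share of infections that become symptomatic, p the days of PCR positivity before onset, and D the days of PCR positivity in an infection that stays asymptomatic. With one swab at a random time in a 30-day interval, and the clock stopping at swab collection, the pre-symptomatic share of scheduled-swab positives labelled asymptomatic is

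(s × p/30) / (s × p/30 + (1 − s) × D/30).

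With s = 0.5 this reduces to p/(p + D):

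| p (days) | D (days) | Share pre-symptomatic |
|---|---|---|
| 2 | 20 | 2/22 = 9% |
| 3 | 15 | 3/18 = 17% |
| 5 | 10 | 5/15 = 33% |

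**Step 3: cross-check with a different denominator.** Take infections that do become symptomatic and are found by a randomly timed swab. The share swabbed before onset is L/(L + A), with L and A the PCR-positive days before and after onset. For L = 1 to 3 and A = 7 to 21 days, this runs from 1/22 = 4.5% to 3/10 = 30%; L = 2 and A = 14 gives 2/16 = 12.5%. This is a share of symptomatic infections, so it should not be set equal to the Step 2 figures. It does show that the error is not negligible under another model.

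**Step 4: does the 4-week look-back need shortening?** Suppose a listed symptom arises from other causes on a share q of days. The chance of at least one in w days is 1 − (1 − q)^w. For q = 0.5%, 1% and 2%:

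| Window | w (days) | Chance of at least one |
|---|---|---|
| 4 weeks before | 28 | 13%, 25%, 43% |
| 14 days before to 14 days after, swab day included | 29 | 13.5%, 25.3%, 44.3% |
| 14 days only | 14 | 7%, 13%, 25% |

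Moving to 14 days on each side gains nothing against unrelated symptoms. It would also miss true onsets 15 to 28 days before a swab. Four weeks roughly matches the 30-day swab interval, so the look-back should stay.

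**Step 5: what does an added 14 days cost in new errors?** Suppose unrelated COVID-like episodes occur at 0.05 to 0.30 per 28 days. The chance of one in 14 days is 1 − exp(−rate × 14/28), or 2.5% to 13.9%. In the middle row of Step 2, of every 18 cases labelled asymptomatic, 3 are pre-symptomatic and 15 are not. The added window would correct the 3 and wrongly move 15 × 0.025 = 0.4 to 15 × 0.139 = 2.1. If any listed symptom counted, at q = 2%, it would wrongly move about 15 × 0.25 = 3.8, more than it corrects.

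**The case against.** The strongest reply has four parts.

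**Later symptoms are not all lost.** An intercurrent illness is an adverse event under Section 6.1. Section 6.4 captures these for 7 days after participation and follows events to resolution or stabilization, and objective 3 uses symptom questionnaires for severity. This stands in part: some of the data would exist. Nothing directs their use in objective 1.

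**The clock may stop later than the swab.** The objective does not say whether it counts from collection or from the result. The footnote to the Section 5.2.1 schedule says a week's samples are tested over the next weekend, so a few days of post-swab symptoms might fall inside the window, or appear on the closing questionnaire. This also stands in part. It would lower the Step 2 shares, but by an amount that depends on laboratory turnaround rather than on a stated rule.

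**The inputs are assumed and the objective is descriptive.** Both are true, and they limit the weight of the point.

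**The added window brings its own errors.** Step 5 shows this is fair. The answer is to report the added group separately, so that nothing in the plan's own split is lost.

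A reader might also infer three stronger things that the documents do not support. The first is that a single headache weeks earlier makes an infection symptomatic. The objective speaks of COVID-19 symptoms, and the list in Section 8 ("fever, cough, SOB, sputum production, anosmia, hyposmia, fatigue, sore throat, nasal congestion, diarrhea, headache") describes data to be captured, not a case definition. At most, an attribution rule is missing. The second is that no survey data exist before enrolment. Section 5.1.1 describes the daily survey as already in active use, and only the study-specific questions are new; whether earlier responses will be linked is not stated. The third is that the look-back is too long and should be cut to 14 days, which Step 4 does not bear out.

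**Conclusion.** The point holds for symptoms that begin after the positive swab. If the plan is followed as written, a pre-symptomatic infection found on a scheduled swab is labelled asymptomatic, and no planned assessment corrects it. On the Step 2 assumptions, 9% to 33% of scheduled-swab positives labelled asymptomatic would be pre-symptomatic. That range assumes half of infections become symptomatic and that the window closes at swab collection.

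The direction of the net bias in the asymptomatic share cannot be read from the documents. Unrelated symptoms in the look-back push the other way: at the Step 5 episode rates, 1 − exp(−rate) gives 4.9% to 25.9% of truly asymptomatic cases with such an episode in 28 days.

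The error is confined to a descriptive secondary objective. The primary endpoint, a positive PCR, does not depend on symptoms.

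**What to change.** In Section 3, with a matching sentence in Section 7.4.3:

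- Keep the 4-week look-back and add 14 days after the first positive swab, counted from the date of collection.
- Record the onset date of each symptom, and name the symptoms that count.
- Report three groups: symptomatic at or before the swab, pre-symptomatic at detection, and asymptomatic throughout. Merging the last two recovers the plan's present split.
- Collect the later symptoms through the existing daily survey or one remote query about 14 days after the positive swab. The survey is addressed to staff currently working in at-risk units, so the query is the safer source for anyone off work.
- State in Section 4.6 that termination for PCR positivity does not cancel this data collection.

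The cost is one extra remote contact per positive participant and a 14-day wait for the final classification. Some unrelated symptoms after the swab will be counted as pre-symptomatic, on the scale shown in Step 5. Onset dates and a named symptom list keep that in view and limit it.
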